10. IMMUNOGENICITY ANALYSES

The immunogenicity analyses will be based on the FA set..

Details of analytical procedures, acceptance criteria, data analysis and reporting for immunogenicity data are described in the immunomonitoring analysis plan.

10.1 Immunogenicity Endpoints and Variables

10.1.1 Secondary Immunogenicity Endpoint

For the characterization of the humoral immune response

- Percentages of subjects with Rabies Specific serum VNTs ≥ 0.5 IU/ml by trial group on Days 1 (pre-vaccination), 15 and 43 and 12, 18*, and 24* months after the last dose.
- Serum geometric mean titers (GMTs) of VNTs by trial group on Days 1, 8, 15, 29, 36, 43, 57, and 91 and 6, 12, 18*, and 24* months after the last dose.

* Will be performed only in subjects with detectable RABV-G-specific IgG at 6 months after the last vaccination.

10.1.2 Exploratory Immunogenicity Endpoints

For the evaluation of the innate immune response:

- Serum cytokine concentrations* including but not limited to chemokine (C-X-C motif) ligand 10, chemokine (CC motif) ligand 3, interleukin-6, tumor necrosis factor- α and interferon- γ at pre-vaccination and 4 hours after vaccination on Day 1, and Days 2 or 3** and 8 after each vaccination.
- Transcriptome profiling* on the day of vaccination at pre-vaccination, and Days 2 or 3** and 8 after each vaccination.

* Will be performed in the first 5 subjects in Group 2 (** on Day 3) and all subjects in Groups 3 and 4 (** on Day 2). Note that Day 3 was planned in the original protocol and only applies to subjects in Groups 1 and 2 who were already enrolled and vaccinated before the last protocol amendment was issued. Day 2 applies to all other subjects.

For the evaluation of antigen specific T-cell response:

- The frequencies and functionalities of RABV-G-specific T cells in peripheral blood from the first 5 subjects in Group 2 and all subjects in Groups 3 and 4 on Days 1, 8, 36, and 91* and 6* and 12* months after the last dose.

* For groups that have shown a significant T-cell response at Day 8 or 36 compared to baseline.

For the evaluation and characterization of the B-cell response

- The frequencies of RABV-G-specific B cells in peripheral blood from the first 5 subjects in Group 2 and all subjects in Groups 3 and 4 on Days 1, 8, 36, and 91* and 6* and 12* months after the last dose.
- The frequencies and activation status of phenotypically distinct subsets of B-cell populations, including but not limited to naïve and memory B cells, plasmablasts, and plasma cells for the first 5 subjects in Group 2 and all subjects in Groups 3 and 4 on Days 1, 8, 36, and 91* and 6* and 12* months after the last dose.
- Sequencing of B-cell receptors of circulating B cells on Days 1, 8, 29, 36, 57, and 91* and 6* and 12* months after the last dose.

* For groups that have shown a significant B-cell response at Day 8 or 36 compared to baseline.

For the characterization of the humoral immune response:

- RABV-G-specific IgM, IgG, and IgA levels measured by enzyme-linked immunosorbent assay on Days 1, 8, 15, 29, 36, 43, 57, and 91 and 6 and 12 months after the last dose.
- RABV-G-specific IgG levels measured by enzyme-linked immunosorbent assay 18* and 24* months after the last dose.
- Identification of epitopes recognized by vaccine-induced antibodies on Days 1, 15, and 43 and 12 months after the last dose**.
- Measurement of RABV-G-specific antibody avidity and affinity on Days 1, 15, and 43 and 12 months after the last dose**.
- Measurement of VNTs against additional heterologous lyssaviruses on Days 1, 15, and 43 and 12 months after the last dose**.

* Will be performed only in subjects with detectable RABV-G-specific IgG at 6 months after the last vaccination.

** Will be performed only on selected samples with VNT >0.5 IU/ml.

10.2 Secondary Immunogenicity Analysis

The number and percentage of subjects with Rabies Specific serum VNTs ≥ 0.5 IU/ml will be determined for each visit and displayed by vaccination group and dose regimen including 95% exact confidence limits. The percentages will be based on subjects providing data for the respective visit.

For evaluation of values below the limit of quantification (=BLQ values) for tables and figures, the following conventions will be made:

- Values <0.1 are identified as BLQ values.
- All concentration values marked as BLQ will be set to $0.5 * \text{LLOQ}$ (= 0.1 IU/ml) = 0.05 IU/ml
- Missing post-dose values will not be replaced.

Absolute (raw untransformed) serum VNT values will be summarized for each visit by vaccination group and dose regimen.

Serum VNT values will be log-transformed and the mean, SD and 95% confidence interval of the log-transformed values will be calculated. The serum GMTs (= antilog mean of log-transformed data) and the corresponding 95% confidence intervals for the GMTs (=antilog lower and upper 95% confidence bound of log-transformed data) as well as geometric SD, median, minimum and maximum will be tabulated by vaccination group and dose regimen for baseline and each postbaseline visit.

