4.2 Endpoints

Primary Endpoints:

- The percentages of subjects with, and the frequencies and intensities of solicited local adverse events (AEs) reported on the day of vaccination and the 7 subsequent days (Days 1-8).
- The percentages of subjects with, and the frequencies, intensities and relationship to vaccination, of solicited systemic AEs reported on the day of vaccination and the 7 subsequent days (Days 1-8).
- The duration (in days) of solicited local AE, of solicited systemic AE and of the individual solicited AEs.
- The percentages of subjects with and frequencies and intensities of any unsolicited and related unsolicited AEs reported on the day of vaccination and the 28 subsequent days (Days 1-29).
- The percentages of subjects with and frequencies and relationship to vaccination, of any serious adverse events (SAEs) and any MAAEs up to 12 months post last dose.
- The percentages of subjects with and frequencies and relationship to vaccination of any adverse events of special interest (AESIs) up to 12 months post vaccination.

Secondary Endpoints:

For safety

- The percentages of subjects with and frequencies of SAEs and MAAEs related to study vaccination from 12 months post last dose up to 24 months post last dose (trial end).
- The percentages of subjects with and frequencies and relationship to vaccination of any AESIs from 12 months post last dose up to 24 months post last dose (trial end).

For the characterization of the humoral immune response

- Percentages of subjects with rabies-specific serum VNTs ≥ 0.5 IU/ml by trial group on Days 1 (pre-vaccination), 15, 43, and 12, 18* and 24* months post last dose.
- Serum geometric mean titers (GMTs) of VNTs by trial group on Days 1, 8, 15, 29, 36, 43, 57, 91, and 6 and 12, 18* and 24* months post-last dose.

* Will be performed only in subjects with detectable RABV-G-specific IgG at 6 months after the last vaccination or Day 91 if the Month 6 blood sample is not available.

Exploratory Endpoints:

For the evaluation of the innate immune response:

- Serum cytokine concentrations* including but not limited to CXCL10, CCL3, IL-6, TNF- α and IFN- γ , at pre-vaccination and 4 hours post-vaccination on Day 1, and Days 2 or 3** and 8 after each vaccination.
- Transcriptome profiling* on the day of vaccination at pre-vaccination, and Days 2 or 3** and 8 after each vaccination.

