9.3 Immunogenicity Assessments

The following immunogenicity assessments will be made:

Rabies-specific serum VNTs will be measured using the WHO-recommended rapid fluorescent foci inhibition test (RFFIT) before and after vaccination on Days 1, 8, 15, 29, 36, 43, 57, 91, and 6, 12, 18 and 24 months post-last dose.

The percentages of vaccine recipients with VNTs ≥ 0.5 IU/ml (WHO-recommended threshold correlating with protective immune responses) will be determined for each trial group. An antibody titer of 0.5 IU/ml serum is viewed as a surrogate of protection and defines seroconversion [26]. GMTs by treatment group will be calculated based on the VNTs on Days 1, 8, 15, 29, 36, 43, 57, 91, and 6, 12, 18 and 24 months post-last dose. VNTs assessments will be performed in a GCP-compliant laboratory.

Note that VNTs assessments at 18 and 24 months after the last vaccination will only be performed in subjects with detectable RABV-G-specific IgG at 6 months after the last vaccination or Day 91 if the Month 6 blood sample is not available.

RABV-G-specific IgM, IgG and IgA serum antibody levels will be measured by enzyme-linked immunosorbent assay (ELISA) on Days 1, 8, 15, 29, 36, 43, 57, 91, and 6 and 12 months post-last dose. In addition, RABV-G-specific IgG serum antibody levels will be measured at 18 and 24 months after the last vaccination in subjects with detectable RABV-G-specific IgG at 6 months after the last vaccination or Day 91 if the Month 6 blood sample is not available.

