Visit 15A may be conducted only in case Visit 15 was conducted as a phone call, and when restrictive measures related to COVID-19 no longer prevent site visits, and the window of Visit 15 has expired. Visit 15A allows the trial procedures, including the blood draws for safety and immunogenicity testing, to occur during a widened visit window starting the day after the expiry of the original visit window and lasting up to 3 months after the original projected visit date (+31-90 days). In that case, all procedures as described in Section 9.4.17.1 for Visit 15, including and blood sampling for safety and immunogenicity assessments, should be performed at Visit 15A.

Also, in case Visit 15 was conducted on site but not all procedures could be performed, Visit 15A should be scheduled on site within the protocol-allowed time interval for Visit 15A (+31-90 days).

If no blood sampling could be performed at Visit 15 and 15A, the end-of-trial blood sample for safety assessment may be performed at Visit 17 (Month 24: Day 729).

9.4.18 *Visit 16 (Month 18: Day 547)*

9.4.18.1 *Visit 16*

The following activities will be performed during Visit 16:

- Safety assessments (SAEs related to study vaccination, MAAEs related to study vaccination, intercurrent medical conditions, AESIs and concomitant medications and vaccinations).
- Blood draw for immunogenicity (only in subjects with detectable RABV-G-specific IgG at 6 months after the last vaccination or Day 91 if the Month 6 blood sample is not available) – VNTs (~18 ml), IgG (~6 ml) (section 9.5.3).

In case Visit 16 cannot take place on site due to the public health emergency related to COVID-19, safety information should be collected via a phone call within the protocol-allowed time interval for Visit 16 (± 30 days).

9.4.18.2 *Optional Visit 16A*

Visit 16A may be conducted only in case Visit 16 was conducted as a phone call, and when restrictive measures related to COVID-19 no longer prevent site visits, and the window of Visit 16 has expired. Visit 16A allows the trial procedures, including the blood draws for immunogenicity testing, to occur during a widened visit window starting the day after the expiry of the original visit window and lasting up to 3 months after the original projected visit date (+31-90 days). In that case, all procedures as described in

Section 9.4.16.1 for Visit 16, including blood sampling for immunogenicity assessment, should be performed at Visit 16A.

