10.3.7 Missing data

Analysis of vaccination variables will be done on a valid case basis, i.e., for missing observations, no imputation for missing data, such as last observation carried forward (LOCF), will be applied. For safety data, some missing or partially missing variables will be imputed as follows:

- For start date:
 - If the AE start date year value is missing, the date uncertainty is too high to impute a rational date. Therefore, if the AE year value is missing, the imputed AE start date is set to missing.
 - If the AE start date year value is less than the treatment start date year value, the AE started before treatment. Therefore:
 - If the AE year is lower than the treatment year and the AE month is missing, the imputed AE start date is set to the mid-year point (i.e., 01JULYYYY).

- If the AE year is lower than the treatment year and the AE month is not missing, the imputed AE start date is set to the mid-month point (i.e., 15MONYYYY).
- If the AE start date year value is greater than the treatment start date year value, the AE started after treatment. Therefore, if the AE year is greater than the treatment year and the AE month is missing, the imputed AE start date is set to the year start point (i.e., 01JANYYYY).
- For resolution date:
 - If date of resolution is completely missing, it is assumed that it resolved at the date of the end of the AE assessment period.
 - If year is present, it is assumed that it resolved on 31 December of that year (i.e., 31DECYYYY), or at the end of the AE assessment period if earlier.
 - If year and month are present, it is assumed that it resolved on the last day of that month, or at the end of the AE assessment period if earlier.

No other safety variables will be imputed. In case the number of missing/partial dates for solicited local AEs, solicited systemic AEs or individual solicited AEs is higher than expected for the analysis of durations (in days), a sensitivity analysis will be conducted to assess the impact on the primary endpoint.

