14.2.1.1 Rabies Specific VNTs >= 0.5 IU/ml by Dosage/Vaccine, Full Analysis Set

		CV7202 1 µg (N = xx)	CV7202 2 µg (N = xx)	CV7202 5 µg (N = xx)	Rabipur (N = xx)
VNTs >= 0.5 IU/ml					
V3 (Day 1)	n	xx	xx	xx	xx
	No	xx (xx.x%)	xx (xx.x%)	xx (xx.x%)	xx (xx.x%)
	Yes	xx (xx.x%)	xx (xx.x%)	xx (xx.x%)	xx (xx.x%)
	95% CI	(xx.x, xx.x)	(xx.x, xx.x)	(xx.x, xx.x)	(xx.x, xx.x)
V5 (Day 8)	n	xx	xx	xx	xx
	No	xx (xx.x%)	xx (xx.x%)	xx (xx.x%)	xx (xx.x%)
	Yes	xx (xx.x%)	xx (xx.x%)	xx (xx.x%)	xx (xx.x%)
	95% CI	(xx.x, xx.x)	(xx.x, xx.x)	(xx.x, xx.x)	(xx.x, xx.x)
V7 (Day 15)	..				
V8 (Day 29)					
V10 (Day 36)					
V11 (Day 43)					
V12 (Day 57)					
V13 (Day 91)					
V14 (Month 6)					
V15 (Month 12)					
V16 (Month 18)					
V17 (Trial End/Month 24)					

CI = Confidence interval (exact Clopper-Pearson confidence interval) for category yes.

VNT >= 0.5 IU/mL = virus neutralization titer threshold according to WHO guideline.

PROGRAM SOURCE: tlfl-###, DATA CUT OFF DATE: DDMMYYYY

RUN DATE: DDMMYYYY hh:mm

Sponsor

Clinical Study Report

Protocol number

Page x of y

14.2.1.2 Rabies Specific VNTs >= 0.5 IU/ml by Dosage/Vaccine and Treatment Group, Full Analysis Set

	CV7202 1x1 µg (N = xx)	CV7202 2x1 µg (N = xx)	CV7202 1x2 µg (N = xx)	CV7202 2x2 µg (N = xx)	
VNTs >= 0.5 IU/ml					
V3 (Day 1)	n No Yes 95% CI	xx xx (xx.x%) xx (xx.x%) (xx.x, xx.x)			
V5 (Day 8)	n No Yes 95% CI	xx xx (xx.x%) xx (xx.x%) (xx.x, xx.x)			
V7 (Day 15)					
V8 (Day 29)					
V10 (Day 36)					
V11 (Day 43)					
V12 (Day 57)					
V13 (Day 91)					
V14 (Month 6)					
V15 (Month 12)					
V16 (Month 18)					
V17 (Trial End/Month 24)					

CI = Confidence interval (exact Clopper-Pearson confidence interval) for category yes.

VNT >= 0.5 IU/mL = virus neutralization titer threshold according to WHO guideline.

PROGRAM SOURCE: tlfl-###, DATA CUT OFF DATE: DDMMYYYY

RUN DATE: DDMMYYYY hh:mm

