14.2.2.3.1 RABV-G Specific Levels of IgG >=780 U/ml by Dosage/Vaccine, Full Analysis Set

Programming note:

Repeat table 14.2.2.1.1 for 14.2.2.3.1 IgG, including V16 (Month 18) and V17 (Month 24) data of subjects with detectable RABV-G specific IgG at 6 months after the last vaccination.

Sponsor
Protocol number

Clinical Study Report
Page x of y

14.2.2.3.2 RABV-G Specific Levels of IgG >=780 U/ml by Dosage/Vaccine and Treatment Group, Full Analysis Set

Programming note:

Repeat table 14.2.2.1.2 for 14.2.2.3.2 IgG, including V16 (Month 18) and V17 (Month 24) data of subjects with detectable RABV-G specific IgG at 6 months after the last vaccination.

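### Month 18 and 24 antibody results come only from subjects selected for detectable IgG, but the VNT tables show them as Full Analysis Set results beside an unselected Month 12

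*SAP*

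**What the plan says.** Protocol 9.3 sets the rule: "Note that VNTs assessments at 18 and 24 months after the last vaccination will only be performed in subjects with detectable RABV-G-specific IgG". The test is made at Month 6, and Protocol 4.2 adds a fallback, "or Day 91 if the Month 6 blood sample is not available". SAP 10.1.1 repeats the restriction for VNT ("Will be performed only in subjects with detectable RABV-G-specific IgG at 6 months after the last vaccination") and SAP 10.1.2 does so for IgG, both without the fallback. Only Months 18 and 24 carry the restriction; Month 12 and earlier visits do not.

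For the summaries, SAP 10.2 states: "The percentages will be based on subjects providing data for the respective visit". SAP 10.3.1 uses the same basis for IgG. Neither section replaces missing values, and Protocol 10.3.7 says that "no imputation for missing data, such as last observation carried forward (LOCF), will be applied".

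VNT shells 14.2.1.1 to 14.2.1.4 are titled Full Analysis Set and run V15, V16 and V17 as consecutive rows under one column N. The responder shells have two footnotes: the exact confidence interval method and "VNT >= 0.5 IU/mL = virus neutralization titer threshold according to WHO guideline". The GMT shells have footnotes on abbreviations, the log transform and the LLOQ. None mentions the selection. The IgG shells do name the subset, "including V16 (Month 18) and V17 (Month 24) data of subjects with detectable RABV-G specific IgG at 6 months after the last vaccination", but only in a programming note. SAP section 12 lists only the removal of the per-protocol sets.

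**The concern.** The secondary endpoint is the percentage of subjects in each trial group with VNT at or above 0.5 IU/ml. The V16 and V17 rows answer a different question: how often that titre is reached among subjects who still had detectable IgG at Month 6. The filter is itself a post-vaccination antibody result, so these subjects are not missing at random. For IgG the selecting assay is also the endpoint assay, with detectable meaning at least 780 U/ml in SAP 10.3.1.

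Two misreadings follow. Within a group, the step from Month 12 to Month 18 changes the denominator, so a row can rise while titres fall. Between groups, there is no distortion where everyone is detectable, and it grows as the detectable share falls, so a weaker regimen can be flattered most. The trial is meant to guide the choice of dose and number of doses, and how long seroprotection lasts bears on that choice.

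**Working it through.** The documents give no Month 18 or 24 rate and no detectable share, so there is no plan figure to reproduce. The illustrations below use the plan's group sizes with assumed counts.

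**Inputs from the documents.** Group sizes are 16 (1 µg), 16 (2 µg) and 11 (Rabipur), from SAP 6.4, with 8 per regimen in Groups 3 and 4. The threshold is 0.5 IU/ml. Values below the LLOQ are set to 0.5 × 0.1 = 0.05 IU/ml. Intervals are 95% Clopper-Pearson.

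**Assumed.** The share detectable, the number of tested subjects at or above 0.5, and the status of untested subjects.

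**General form.** Let s be the share tested, and pS and pU the rates at or above 0.5 IU/ml in tested and untested subjects. The table shows pS; the all-subject rate is s·pS + (1 − s)·pU. The difference is (1 − s)(pS − pU). With pS = 75%, in percentage points:

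| s | pU = 0% | pU = 25% | pU = 50% | pU = 75% |
|---|---|---|---|---|
| 1.00 | 0 | 0 | 0 | 0 |
| 0.75 | 18.75 | 12.5 | 6.25 | 0 |
| 0.50 | 37.5 | 25.0 | 12.5 | 0 |
| 0.25 | 56.25 | 37.5 | 18.75 | 0 |

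If pU = 0, the shown rate is the all-subject rate multiplied by 1/s: 1.0, 1.33, 2 and 4 for s = 1.00, 0.75, 0.50 and 0.25.

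**Within one group.** Take 16 subjects, 8 of them IgG-detectable, all with Month 12 data.
- Month 12, all subjects: 7/16 = 43.8% (19.8 to 70.1). All 7 are assumed to be in the detectable subset.
- One subject falls below 0.5 by Month 18. The planned row is 6/8 = 75.0% (34.9 to 96.8), an apparent rise.
- All subjects, untested counted as below 0.5: 6/16 = 37.5% (15.2 to 64.6), a fall.
- Same subset at both visits: 7/8 = 87.5% to 6/8 = 75.0%, also a fall.

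**Bounds and break-even.** If none or all of the 8 untested are at or above 0.5, the all-subject rate lies between 6/16 = 37.5% and 14/16 = 87.5%. The shown rate is too high exactly when pU < pS, here when fewer than 6 of the 8 untested are at or above 0.5.

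**Between groups.** Suppose all 11 Rabipur subjects are detectable and 10/11 = 90.9% reach 0.5. The gap to the group above is 90.9 − 75.0 = 15.9 points as planned, and 90.9 − 37.5 = 53.4 points with the untested below 0.5. This is the extreme case.

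**One regimen of 8.** With 4 detectable and 3 at or above 0.5, the table shows 3/4 = 75.0% (19.4 to 99.4), against 3/8 = 37.5% (8.5 to 75.5); the bounds are again 37.5% to 87.5%.

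**GMT.** With 8 of 16 tested and a tested GMT of 1.0 IU/ml, the all-subject GMT is the square root of (1.0 × the untested GMT). It is 0.22, 0.45 or 0.70 IU/ml if the untested are at 0.05, 0.2 or 0.49, so the planned figure is 4.5, 2.2 or 1.4 times higher.

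**The case against.** The SAP follows the protocol. The restriction is attached to the Month 18 and 24 endpoints, the protocol asks for valid-case analysis, and SAP 10.1.1 discloses the rule. Tested-only summaries are therefore no departure, and section 12 had no duty to mention them. This stands, and those summaries should stay. It does not remove the gap, because the disclosure does not reach the VNT tables.

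The shells print N, n and the number of responders, so a reader can divide responders by N, and the listings give individual values. That yields only the worst-case rate. It does not show why n fell, and other losses are possible: Protocol 9.4.17.2 already provides for the case "If no blood sampling could be performed at Visit 15 and 15A", and COVID-19 could also prevent later visits.

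The effect is limited. The trial is descriptive, two of twelve VNT time points are affected, and Month 12 is free of the IgG restriction. That caps the seriousness, but in a descriptive trial the tables are the result. SAP section 6 already uses footnotes to state the percentage basis in special tables.

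Direction and size are not shown by the documents. IgG ELISA and VNT are different assays, and the bounds above include the planned 75%. This is correct, and the conclusion is conditional for that reason. The immunomonitoring analysis plan, to which SAP section 10 refers, was not available; any handling there should be cross-referenced.

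**Conclusion.** The concern holds. As written, the plan reports persistence among IgG-selected subjects as a by-group Full Analysis Set result next to an unselected Month 12 row. The VNT tables carry no reader-facing label, and no response rate over all subjects is given. For IgG, the subset is named only to the programmer.

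The missing label and the omitted Day 91 fallback follow from the text alone; the latter is a separate wording mismatch that matters only for subjects without a Month 6 sample. The overstatement needs two conditions: some subjects must be IgG-undetectable, and they must reach 0.5 IU/ml less often than those tested. The second is likely, since both assays measure antibody to the same antigen, but it is not established. If every subject is detectable, the effect is zero. At 50% detectable with 75% of tested subjects at or above threshold, it ranges from 0 to 37.5 points as the untested rate goes from 75% down to 0.

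**What to change.** - Keep the tested-only V16 and V17 summaries. Add a footnote to the VNT and IgG tables stating that these rows cover subjects IgG-detectable at Month 6, or at Day 91 if Month 6 is unavailable.
- Add Month 12 results in that same subset.
- Add, for V16 and V17, the percentage with VNT at or above 0.5 IU/ml among all Full Analysis Set subjects still in follow-up, counting those not sampled because of undetectable IgG as below 0.5. Show subjects missing for other reasons separately, and give best- and worst-case bounds. Do the same for IgG at or above 780 U/ml.
- Give the GMT with IgG-undetectable subjects set to 0.05 IU/ml as a sensitivity analysis only.
- Check the assumption against the Month 6 and Month 12 VNTs of IgG-undetectable subjects, which the trial already collects.
- Declare the additions in SAP section 12 as supplementing the no-imputation rule of Protocol 10.3.7, and align SAP 10.1.1, 10.1.2 and the IgG shell notes with the Day 91 fallback.

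The cost is text in SAP sections 10 and 12, a footnote and a few table rows, with no new samples or visits. Late rates may look less favourable, and the all-subject row rests on an assumption, which is why the bounds must accompany it.

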4. TRIAL DESIGN AND PLAN

This is a non-randomized, open label, controlled, dose-escalation, phase I clinical trial to evaluate the safety, reactogenicity, and immunogenicity of 1 or 2 i.m. administrations of candidate rabies messenger ribonucleic acid (mRNA) vaccine CV7202 in healthy adult subjects.

Subjects will be enrolled in 2 trial sites, 1 in Germany, 1 in Belgium.

Approximately 52 subjects will be enrolled sequentially in up to 4 trial groups to receive either a dose of CV7202 containing different mRNA content or Rabipur. In a first CV7202 group, 10 subjects have received a dose containing 5 µg mRNA. A dose of 1 or 2 µg mRNA will be administered to 2 additional groups of 16 subjects each, of whom 8 in each group will be administered a second dose 28 days later. A control group of 10 subjects will receive 3 doses of the licensed vaccine Rabipur according to the manufacturer's recommendations. Safety and immunogenicity assessments will be made up to 2 years following the last dose administration.

Specified safety data will be reviewed by an internal safety review committee and a data safety monitoring board on a pre-defined schedule. At each planned safety review, safety data will be reviewed, and a GO/NO GO decision made accordingly for enrollment of further subjects and administration of subsequent doses.

Enrollment will be staggered in Groups 2 to 4 to ensure the safety of the participating subjects. Enrollment into Group 1 (1.0 ml Rabipur) will not be staggered, since the clinical safety of Rabipur is well established.

Subjects will be enrolled at pre-screening (Day -90 to -1) to receive either CV7202 starting on Day 1 as 1 dose or 2 doses (at least 28 days apart), or 3 doses of control vaccine (Rabipur). Follow-up for safety and immunogenicity is planned up to 24 months after the last dose; therefore, the expected duration of participation for each subject is approximately 24 months after the last dose.

Please refer to protocol section 5 for more details of trial design, protocol section 6 for trial population and protocol section 7 for discontinuation/withdrawal criteria.

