10.3 Exploratory Analyses

10.3.1 Immunoglobulin

The number and percentage of subjects with detectable RABV-G-specific immunoglobulin ($> \text{LLOQ}$: IgM $\geq 780 \text{ U/ml}$, IgA $\geq 195.5 \text{ U/ml}$ and IgG $\geq 780 \text{ U/ml}$) levels will be determined for each visit and displayed by vaccination group and dose regimen including 95% exact confidence limits. The percentages will be based on subjects providing data for the respective visit.

For evaluation of values below the limit of quantification (=BLQ values) for tables and figures, the following conventions will be made:

- Values <LLOQ are identified as BLQ values.
- All concentration values marked as BLQ will be set to $0.5 * \text{LLOQ}$ (LLOQs: IgM 780 U/ml, IgA 195.5 U/ml, IgG $\geq 780 \text{ U/ml}$)
- Missing post-dose values will not be replaced.

Absolute (raw untransformed) RABV-G-specific IgM, IgG and IgA levels will be summarized for each visit by vaccination group and dose regimen.

RABV-G-specific immunoglobulin levels will be log-transformed and the mean and 95% confidence interval of the log-transformed values will be calculated. The GMTs (= antilog mean of log-transformed data) and the corresponding 95% confidence intervals for the GMTs (=antilog lower and upper 95% confidence bound of log-transformed data) as well as geometric SD, median, minimum and maximum will be tabulated by vaccination group and dose regimen for baseline and each postbaseline visit.

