14.2.1.3 Rabies Specific VNTs (IU/mL) by Dosage/Vaccine, Full Analysis Set

	CV7202 1 µg (N = xx)	CV7202 2 µg (N = xx)	CV7202 5 µg (N = xx)	Rabipur (N = xx)
V3 (Day 1)	n xx	xx	xx	xx
	GMT (SD) xx.x (xx.xx)	xx.x (xx.xx)	xx.x (xx.xx)	xx.x (xx.xx)
	95% CL (xx.x, xx.x)	(xx.x, xx.x)	(xx.x, xx.x)	(xx.x, xx.x)
	Median xx.x	xx.x	xx.x	xx.x
	Min, Max xx, xx	xx, xx	xx, xx	xx, xx
V5 (Day 8)	n xx	xx	xx	xx
	GMT (SD) xx.x (xx.xx)	xx.x (xx.xx)	xx.x (xx.xx)	xx.x (xx.xx)
	95% CL (xx.x, xx.x)	(xx.x, xx.x)	(xx.x, xx.x)	(xx.x, xx.x)
	Median xx.x	xx.x	xx.x	xx.x
	Min, Max xx, xx	xx, xx	xx, xx	xx, xx
V7 (Day 15)	..			
V8 (Day 29)				
V10 (Day 36)				
V11 (Day 43)				
V12 (Day 57)				
V13 (Day 91)				
V14 (Month 6)				
V15 (Month 12)				
V16 (Month 18)				
V17 (Trial End/Month 24)				

GMT = Geometric mean titer, CL = Confidence limit.

Data are log-transformed, mean, SD and 95% CLs calculated and antilog of mean, SD and 95% CLs tabulated.

Titers marked as below lower limit of quantification (LLOQ=0.1 IU/mL) are set to 0.5*LLOQ.

PROGRAM SOURCE: tlf-###, DATA CUT OFF DATE: DDMMYYYY

RUN DATE: DDMMYYYY hh:mm

Sponsor

Clinical Study Report
Page x of y

Protocol number

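### The GMT intervals treat substituted BLQ values as measured: zero width when every value is BLQ, and coverage well below 95% once BLQ values strongly predominate

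*SAP*

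**What the plan says.** SAP 10.2 defines the limit ("Values <0.1 are identified as BLQ values") and the substitution ("All concentration values marked as BLQ will be set to" half the LLOQ, which is 0.05 IU/ml). Then: "Serum VNT values will be log-transformed and the mean, SD and 95% confidence interval of the log-transformed values will be calculated". The antilogs "will be tabulated by vaccination group and dose regimen for baseline and each postbaseline visit".

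The footnotes of shell 14.2.1.3 repeat both steps: "Data are log-transformed, mean, SD and 95% CLs calculated and antilog of mean, SD and 95% CLs tabulated" and "Titers marked as below lower limit of quantification (LLOQ=0.1 IU/mL) are set to 0.5*LLOQ". Shells 14.2.1.3 and 14.2.1.4 have rows for n, GMT (SD), 95% CL, median, and minimum and maximum. They have no row for the number of BLQ values and no rule for SD = 0.

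SAP 10.3.1 applies the same method to the immunoglobulins: "RABV-G-specific immunoglobulin levels will be log-transformed and the mean and 95% confidence interval of the log-transformed values will be calculated". Their LLOQs are 780 (IgM), 195.5 (IgA) and 780 (IgG) U/ml. Separate Ig tables give the number and percentage of subjects at or above exactly those values.

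The SAP does not say whether the interval uses the t or the normal distribution. It gives no method for censored data. SAP 10 refers details of data analysis and reporting to an immunomonitoring analysis plan, which was not available for this review.

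**The concern.** A BLQ titre says only that the value lies below 0.1. Once each one is replaced by 0.05, the SD formula sees identical measurements, and the interval shrinks as the information about the titre gets poorer.

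Cells dominated by BLQ values are to be expected. Protocol 6.2 excludes anyone who has had a rabies vaccine, so most Day 1 titres should be BLQ. Day 8 and low-dose cells may also be low. The VNT GMT by group and visit is a named secondary endpoint, and the protocol synopsis gives selection of the dose and number of doses as the trial's purpose. A reader comparing weak responses would see limits labelled 95% that are far too narrow or in the wrong place.

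**Working it through.** **Inputs from the documents.** LLOQ 0.1 IU/ml, substituted value 0.05 and confidence level 95% (SAP 10.2). Group sizes come from SAP 4: "2 additional groups of 16 subjects each, of whom 8 in each group will be administered a second dose 28 days later". That gives n = 16 per dose group and n = 8 per regimen, with 10 subjects at 5 µg. SAP 6.4 reports 11 vaccinated with Rabipur.

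**Assumptions.** The documents give neither the SD nor the BLQ share. Log10 titres are taken as normal with SD 0.3 to 0.8, and the BLQ share p is varied. The interval is read as a t-interval on the log scale: mean ± t(0.975, n−1) × SD/√n, then antilog.

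**Plan's own figures.** 0.5 × 0.1 = 0.05 IU/ml reproduces. With essentially no BLQ values, simulated coverage is 0.949 to 0.951, so the nominal level also reproduces.

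**All values BLQ.** Every log value is log10(0.05) and SD = 0. The table prints GMT 0.05, geometric SD 1 and limits (0.05, 0.05), with t or z and at any n. The Ig equivalents are 0.5 × 780 = 390 and 0.5 × 195.5 = 97.75 U/ml. If each subject is BLQ independently with probability p, the chance of such a cell is pⁿ:

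| p | n = 8 | n = 10 | n = 16 |
|---|---|---|---|
| 0.90 | 43% | 35% | 19% |
| 0.95 | 66% | 60% | 44% |

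**One quantifiable value.** Take n = 8 with one titre of 0.2 and seven BLQ. The log distance from the floor is log10(0.2/0.05) = 0.602. The log mean is −1.301 + 0.602/8 = −1.226, so GMT = 0.059. The standard error is 0.602/8 = 0.075 and t = 2.365. The limits are 10^(−1.226 ± 0.178) = 0.039 to 0.090. A single value sets both the centre and the width.

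**Coverage of the true GMT.** 100,000 simulated groups per setting; each entry is the range over n = 8, 10 and 16:

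| BLQ share | SD 0.3 | SD 0.4 | SD 0.5 | SD 0.6 | SD 0.8 |
|---|---|---|---|---|---|
| 50% | 0.92 | 0.94 | 0.94–0.95 | 0.93–0.94 | 0.88–0.94 |
| 60% | 0.91–0.92 | 0.94 | 0.91–0.94 | 0.84–0.93 | 0.61–0.89 |
| 75% | 0.90–0.94 | 0.80–0.87 | 0.12–0.74 | 0.00–0.28 | 0.00–0.04 |
| 80% | 0.82–0.94 | 0.13–0.72 | 0.00–0.13 | 0.00–0.02 | 0.00 |
| 90% | 0.00–0.13 | 0.00 | 0.00 | 0.00 | 0.00 |

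**Coverage of the mean of the substituted values.** This target needs no assumption about titres below the limit being recovered: 0.90–0.94 at 60% BLQ, 0.84–0.91 at 75%, 0.80–0.90 at 80%, 0.57–0.82 at 90% and 0.34–0.56 at 95%.

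**Source of the loss.** The true GMT is 10^(−1 − z_p × SD), where z_p is the standard normal quantile of p. At 90% BLQ and SD 0.5 it is 10^(−1 − 1.2816 × 0.5) = 0.023. The mean of the substituted log values is 0.9 × (−1.301) + 0.1 × (−1.641) + 0.5 × 0.1755 = −1.247, which is 0.057. The ratio is about 2.5. At 75% BLQ it is about 0.071 against 0.046, or 1.5. Because this is bias, more subjects make coverage worse: 0.74 at n = 8 and 0.12 at n = 16 for 75% BLQ and SD 0.5.

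The substituted value always lies log10(2) below the limit. Under the same SD and BLQ share, these coverages therefore apply to the Ig tables as well.

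**The case against.** The strongest case against has five parts.

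- **The analysis is descriptive.** SAP 6 rules out confirmatory inference, and no between-group GMT contrast is planned. That limits the consequence, but an interval labelled 95% should still behave roughly as one.
- **Much can already be seen.** The substitution is footnoted, a median of 0.05 shows that at least half the values are BLQ, a maximum of 0.05 shows that all are, and individual titres are listed. This stands in part: the reader still cannot get the BLQ share. The ≥0.5 IU/ml table does not supply it, because its No row mixes BLQ values with titres from 0.1 up to 0.5.
- **The true GMT in these cells lies below the assay limit**, so its value rests on extrapolating a lognormal curve, which is doubtful for unvaccinated sera. This is fair, and it is why the second target was computed. Coverage at 90% BLQ is still only 0.57 to 0.82.
- **The interval type is not named and the immunomonitoring plan was not seen.** Both are true. A normal quantile gives lower coverage in nearly every setting, and the SAP shells, which fix what is printed, contain no remedy.
- **The late visits are less exposed.** SAP 10.1.1 restricts Month 18 and 24 testing to subjects with detectable IgG at Month 6.

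Three stronger readings are tempting, and the documents support none of them. A reader might infer that the intervals fail whenever most values are BLQ. At 60% BLQ with SD 0.3 to 0.5 coverage is 0.91 to 0.94, and at 75% it runs from 0.94 to 0 depending on an SD that is not given. A reader might infer that the Ig tables also hide the BLQ count. They do not, since their thresholds are the LLOQs and the No row is that count. A reader might infer that the protection endpoint is compromised. It is not: 0.05 and any value below 0.1 fall on the same side of 0.5.

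**Conclusion.** The point holds as a minor one. The zero-width interval in an all-BLQ cell is exact arithmetic and plausible at Day 1. Coverage well below 95% sets in at roughly 80 to 90% BLQ, earlier if the SD is large and later if it is small. At 90% BLQ it appears for every group size, SD and target examined.

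The coverage figures rest on normal log10 titres, an assumed SD of 0.3 to 0.8 and a t-interval. Against the true GMT the main cause is the 0.05 floor, so in such cells the printed GMT is unreliable as well as its limits. Half-LLOQ substitution itself need not be abandoned. The exact limits for the percentage at or above 0.5 IU/ml are unaffected.

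**What to change.** Keep the 0.5 × LLOQ rule and make these display changes:

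1. Add a row *n (%) BLQ* to VNT shells 14.2.1.3 and 14.2.1.4. The Ig GMT tables need no such row.
2. In the VNT and Ig GMT tables, when all values in a cell are BLQ (SD = 0), print the GMT as *<LLOQ* with no interval.
3. When BLQ values strongly predominate, for example 75% or more, give the median and range with BLQ values shown as *<LLOQ*, and omit the GMT interval. If a GMT stays in such a cell, footnote that it cannot fall below the substituted value.
4. State in SAP 10.2 and 10.3.1 which distribution the interval uses.

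The 75% cut-off is a judgement and should be fixed in advance. A cut-off at half would remove intervals that still work for moderate SDs.

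A left-censored normal likelihood is optional only. In simulation it covered 0.92 to 0.97 when at least two titres were quantifiable. At 75% BLQ that condition failed in 37 to 39% of data sets with n = 8 and about 6% with n = 16.

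The cost is one table row and one display rule, with no new data and no endpoint change. The downside is that some cells will have no interval.
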